**23. ECONOMIC BURDEN TO SUBJECTS**

**24. PROCESS TO DOCUMENT CONSENT IN WRITING**

**25. DRUGS AND DEVICES**

**26. REFERENCES**

## 1.0 STUDY SCHEMA

## 2.0 INTRODUCTION

### 2.1 STUDY OVERVIEW

In this single arm pilot study, patients with advanced solid tumors and moderate-to-severe pain who are not already on high-dose opioids will be prospectively assigned to early referral to an anesthesia-trained interventional pain management specialist. Specialists all practice at the Brigham and Women's Hospital or its affiliated clinics (e.g., at [name], Faulkner Hospital, or Foxboro). These clinicians have a strong affiliation with the Dana-Farber Cancer Institute, and have extensive experience in managing cancer pain with a variety of interventional pain management procedures (e.g. celiac or hypogastric plexus blocks, intrathecal TDD).

Patients will be evaluated for interventional pain management strategies (including, but not limited to, nerve blocks and intrathecal TDD); they will be followed longitudinally with frequent reassessment and management guided by a standardized treatment pathway. This pathway is designed to make the intervention transferrable and ultimately scalable if it is proved effective.

Patients will be followed for 4 months with monthly surveys, and the option to report daily symptoms using a HIPPA-compliant pain-tracking smartphone application. Study staff will also complete structured chart abstractions at end-of-study to assess pain management interventions, opioid use, and healthcare utilization (e.g. hospitalizations/ED visits for pain), and survival.

Primary outcomes of this pilot study will relate to feasibility and acceptability, including recruitment and retention rates, number of completed interventional pain management consultations, the types of interventions offered and the proportion of patients accepting those interventions, and patients' satisfaction with the intervention. We will also explore time trends in clinically relevant outcomes including pain severity/interference, physical functioning, QOL, opioid dose, healthcare utilization and survival.

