**Health systems factors likely play a significant role in limiting advanced cancer patients' access to interventional pain management.** First, there are no standardly agreed upon triggers for intervention pain management referral, leading to very late referrals when patients may not even be eligible for certain procedures such as TDD. Second, most interventional pain management specialists operate outside of cancer clinics, making oncologists largely unfamiliar with their capabilities and scope of practice. Third, many pain management specialists lack specific experience with advanced cancer patients, or guidelines needed to integrate interventional techniques into these patients' care. These barriers call for healthcare delivery research to evaluate specific referral processes and treatment algorithms to integrate interventional strategies into the care of advanced cancer patients.

PROTOCOL TITLE: Randomized Clinical Trial of Early Intervention Pain Management for Patients with Advanced Cancers  
Version 4.0, [October 27, 2023]

Our overarching hypothesis is that early referral to pain management specialists and systematic consideration of interventional pain management strategies, will improve pain severity, physical functioning, and quality of life among patients with pain from advanced solid malignancies. We also hypothesize that early referral will minimize patients' reliance on systemic opioids, reduce opioid toxicity, unplanned emergency department and hospital-based care for pain, and potentially prolong survival.

This will be a single arm pilot study in which we will identify patients with advanced malignancies who have cancer-related pain, who are not yet on high-dose opioids, and we will arrange for early referral to an interventional pain management specialist at a large center with expertise in cancer pain management. We will evaluate metrics of study feasibility/acceptability needed to plan for a future randomized trial. We will also assess key proximal and distal outcomes needed for a future randomized trial, such as time to completion of the pain management referral, the numbers and types of interventional pain strategies recommended (e.g. nerve blocks, ITT), the proportion of patients accepting those therapies, trajectories of pain severity/interference, opioid doses, and pain-related ED visits and hospitalizations.

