### **6.2. Selection of Instruments**

*Feasibility:* As the primary goal of this study is to assess feasibility of the early intervention pain management intervention, our study team will track the following measures of feasibility

- Feasibility of recruitment: we will track the number of patients screened, the number approached, the proportion who consent to the study (and reasons for study refusal)
- Feasibility of the intervention: we will track the following
  - o Proportion of participants who undergo a consultation with an interventional pain specialist, and the proportion who do so within the target timeframe of 4-weeks
  - o Proportion of participants who are offered an interventional pain procedure, and the type of procedure offered (e.g. nerve block, steroid injection, epidural or intrathecal pump)
  - o Proportion of participants offered a procedure who accept the procedure, who undergo that procedure, and the timeframe of the procedure
  - o Proportion of patients who receive more than one pain intervention
- Feasibility of study assessments: We will keep track survey response rates and reason for non-completion
- Feasibility of retention: We will track the number of patients who complete the study, and reasons for drop-out

PROTOCOL TITLE: Randomized Clinical Trial of Early Intervention Pain Management for Patients with Advanced Cancers  
Version 4.0, [October 27, 2023]

**Survey assessments** will occur at baseline, 2-months, and 4-months. Measures are selected because we expect them to be covariates, primary or secondary outcomes of a future efficacy study.

*Pain severity:* pain severity will be assessed by averaging the least/average/worst pain rating from the Brief Pain Inventory (BPI) short-form (0-10 numeric rating scale, NRS). *Pain interference:* interference of pain on patients' general activity, mood, walking ability, work, relationships, sleep, and enjoyment of life will also be assessed by the BPI short-form (0-10)

*Quality of life:* will be assessed with the Functional Assessment Cancer Therapy: General (FACT-G) including its physical wellbeing, social/family wellbeing, emotional wellbeing, and functional wellbeing subscales.

*Anxiety and depression:* will be measured using the 4-item PROMIS depression short-form, and 4-item PROMIS anxiety short form

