*Opioid-use:* patients' opioid and non-opioid analgesic regimen will be abstracted from the chart at baseline and end-of-study. Patients will also be asked to report on adherence to scheduled pain medications and the number of breakthrough opioid doses they take in a day

*Symptoms:* the Patient-Reported Outcomes version of the Common Terminology Criteria for Adverse Events (PRO-CTCAE™) will assess relevant symptoms most relevant to pain or opioid side effects including constipation, concentration, fatigue, insomnia.

*Pain Catastrophizing:* This will be measured from the 13-item pain catastrophizing scale

*Care satisfaction:* 5-items adapted from the Hospital Consumer Assessment of Healthcare Providers and Systems will assess satisfaction with pain management care. Patients will also be asked whether they received any interventional pain procedures, and if so – how much relief they received for their pain.

Healthcare utilization will be assessed through structured chart abstraction (see Appendices BA and BB)

- Pain-related ER visits

PROTOCOL TITLE: Randomized Clinical Trial of Early Intervention Pain Management for Patients with Advanced Cancers  
Version 4.0, [October 27, 2023]

- Pain-related hospitalization, unplanned and planned
- Intervention types, location, results,
- Interventions – if placement of a TDD pump - report catheter tip location, complications, medication and dose at the time of implant and at end-of-study, any related procedures required.

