### 7.3. Data Collection:

Three survey assessments (at baseline, 2-months, and 4-months) will assess future outcomes and covariates needed to plan a future randomized clinical trial, including patients' pain, functional wellbeing, and quality of life. The daily symptom reporting using a smartphone platform will enable

PROTOCOL TITLE: Randomized Clinical Trial of Early Intervention Pain Management for Patients with Advanced Cancers  
Version 4.0, [October 27, 2023]

exploratory longitudinal analyses of response to pain procedures. Structured chart abstractions will assess treatment compliance, opioid prescribing, changes in pain management, and healthcare utilization (i.e. hospitalization, ED visits).

Survey assessments: Patient will complete surveys at baseline, 2 months and 4 months. We anticipate pre-post differences in pain severity scores from baseline to 4 months to be our future primary outcome in a randomized clinical trial. 4 months is a relevant timeframe, because we anticipate it will be sufficient for a patient to be evaluated and treated with at least one interventional pain procedure, and any needed secondary procedures if response is insufficient.

The baseline survey will assess socio-demographics, characteristics and severity of pain, symptom burden and quality of life, and psychological characteristics known to influence pain (e.g. pain catastrophizing, perceived stress, anxiety, depression, sleep). Subsequent surveys will be brief and will focus on pain severity, functional interference, and quality of life.

7.3.1. Structured chart abstractions: A study assistant will abstract clinical characteristics at baseline (e.g. tumor type and location of metastases, date of diagnosis, current treatment). At the end of study, the RA will also conduct a detailed abstraction to evaluate the following (see appendices BA and BB):

- Any interventional pain management procedures, and dates of procedures
- Opioid doses (MMEDs) and dates of medication changes
- Unplanned and planned hospitalizations for pain
- Emergency department visits for pain
- Survival (which will be augmented by the National Death Index, which is integrated into the DFCI research database OnCORE through an existing process)

7.3.2. Smartphone based symptom reporting: \* As described in section 6.2, this is not applicable to patients recruited to the study after April 4th, 2023.

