## 9. Statistical Analysis and Sample Size

Power calculations are inappropriate for this pilot feasibility study. We plan to enroll 31 patients over a 6-month period, with 4 additional months for follow-up and 2 months for study preparation and data analysis – based upon projections of clinical volume.

The primary purpose of our analysis is to examine feasibility and acceptability of the intervention. Benchmarks of feasibility/acceptability are as follows

1. Proportion of patients assigned to the intervention that undergo an interventional pain consultation within 4 weeks:  $\geq 80\%$
2. Among patients referred and evaluated by an anesthesia pain specialist, at least 50% will agree and ultimately receive at least one interventional pain procedure
3. Satisfaction with the intervention: At least 80% of patients will be satisfied with the quality of care received in the interventional pain management clinic, defined as rating it a 7 or above on a 0-10 scale.

Analyses will be conducted using an intent-to-treat analysis. Pre-post differences will be assessed and univariate and multivariate descriptive analyses will be performed on all the dependent variables. Statistical significance will be set at  $p < 0.05$ . Chi-square, t-tests, and logistic regression and cluster analyses will be conducted as appropriate. We will calculate the proportion of participants meeting feasibility benchmarks with 95% confidence intervals. Pre-post differences in pain severity (primary outcome) will be examined using a one-sample t-test. One-sample t-tests will also examine pre-post differences in pain interference scores, QOL scores (using the FACT-G), QOL subscales (e.g. physical wellbeing, functional wellbeing), depression/anxiety scores, and opioid MMEs. We will also calculate the proportion of patients undergoing dichotomous outcomes (e.g. occurrence of pain-related ED visits), and the proportion alive at end-of-study. Participants will also be consented for mortality follow-up to allow for examination of survival data.

Missing data will be imputed using a last observation carried forward principle, which will be greatly enhanced by the inclusion of smartphone symptom tracking.

PROTOCOL TITLE: Randomized Clinical Trial of Early Intervention Pain Management for Patients with Advanced Cancers  
Version 4.0, [October 27, 2023]

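### Time trends are promised for survey outcomes, but Section 9 models a trajectory only for app-reported pain, leaves the post visit undefined and names no longitudinal analysis of the 2-month survey

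*Combined protocol and SAP*

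**What the plan says.** **The promise.** Section 2.1 says: "We will also explore time trends in clinically relevant outcomes including pain severity/interference, physical functioning, QOL, opioid dose, healthcare utilization and survival". Section 2.2 lists "trajectories of pain severity/interference, opioid doses" among the outcomes needed to plan a future randomized trial.

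**The data.** Section 6.2 says surveys "will occur at baseline, 2-months, and 4-months". Table 3 and Section 7.1 agree, and Table 3 places the BPI and FACT-G at all three visits. Section 2.1 alone says "Patients will be followed for 4 months with monthly surveys". For opioids, Section 6.2 says the regimen "will be abstracted from the chart at baseline and end-of-study", while the end-of-study abstraction in Section 7.3.1 records "Opioid doses (MMEDs) and dates of medication changes".

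**The analysis.** Section 9 says: "Pre-post differences in pain severity (primary outcome) will be examined using a one-sample t-test". It names the same test for interference, FACT-G and its subscales, depression/anxiety and opioid MMEs. It does not say which visit is post. The baseline-to-4-month interval comes from Section 7.3, which describes the later trial: "We anticipate pre-post differences in pain severity scores from baseline to 4 months to be our future primary outcome". Missing values are filled by last observation carried forward. The one longitudinal model in Section 9 is a linear regression of pain from the smartphone reports. Section 6.2 describes that app as optional and not offered to participants recruited after April 4, 2023.

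**The concern.** A single pre-post difference cannot describe a trend. For interference, QOL and opioid dose, the trends promised in Sections 2.1 and 2.2 have no clearly matching longitudinal analysis in Section 9. For pain severity, the match covers only app users, an early-recruited and self-selected subset whose size the documents do not give.

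The shape of the course matters to the pilot's purpose. Section 7.2 anticipates that some patients will respond, then develop new or recurrent pain, and be considered for further procedures. Section 7.3 justifies the 4-month point partly by the time needed for secondary procedures. Whether the average cohort improves early and then partly loses ground, or improves late, is useful when planning the next trial. The 2-month survey is the measure collected from all participants that bears on this.

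Leaving the post visit undefined adds a second problem. Under carry-forward, a 2-month score can enter the t-test as if it had been measured at the later visit.

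**Working it through.** The documents give no SD, correlation, effect size or dropout figure, and N = 31 rests on clinical volume, so there is no figure of the plan to reproduce. The mean courses, SDs, correlations and missing fractions below are assumptions.

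**1. Which named analysis uses the 2-month survey?**

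| Outcome | Collected | Named analysis in Section 9 | Use of 2-month value |
|---|---|---|---|
| BPI severity | 0, 2, 4 months; app | t-test on pre-post; linear regression on app pain | Carry-forward only |
| BPI interference | 0, 2, 4 months; app | t-test on pre-post | Carry-forward only |
| FACT-G | 0, 2, 4 months; not in app | t-test on pre-post | Carry-forward only |
| Opioid MME | Chart, with dated changes | t-test on pre-post | Not a survey measure; dated changes unused |

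**2. Does the planned difference show the course?** Take mean pain at 0, 2 and 4 months.

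- Course A, 6-4-5: 4-month change = 5 - 6 = -1.0; 2-to-4-month change = 5 - 4 = +1.0.
- Course B, 6-6-5: 4-month change = 5 - 6 = -1.0; 2-to-4-month change = 5 - 6 = -1.0.

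The planned test gives the same mean change for both. The 2-to-4-month change has opposite signs.

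**3. Would a straight-line slope on the survey scores help?** With times 0, 2, 4 the deviations from the mean time are -2, 0, +2, and their squares sum to 8. The slope is (-2·y0 + 0·y2 + 2·y4)/8 = (y4 - y0)/4, which is -0.25 per month for both courses. With complete, equally spaced visits the 2-month value drops out, so visit must be a category.

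**4. What does carry-forward do?** Suppose a fraction f of 4-month scores is missing, the 2-month score is carried forward, and those patients follow the same mean course. The true change is -1.0 in both.

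- Course A: (1 - f)(-1) + f(-2) = -1 - f. For f = 10% to 40% this is -1.1 to -1.4.
- Course B: (1 - f)(-1) + f(0) = -1 + f. For the same f this is -0.9 to -0.6.

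The 2-month data can thus move the test, in a direction set by the course that the test does not display.

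**5. Is the 2-to-4-month change estimable with this sample?** The 95% half-width is t(n-1) × SD × √(2(1 - rho)) / √n, where rho is the correlation between visits. For n = 31, t = 2.042. With SD 2.0 and rho 0.5 this is 2.042 × 2.0 × 1.0 / 5.568 = 0.73 points. Over SD 1.5 to 2.5 and rho 0.3 to 0.7 it runs from 0.43 to 1.09 points. With 20 complete pairs it runs from 0.54 to 1.38. That is adequate for an exploratory estimate if the change is about 1 point or more, though not in every case.

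**6. Does the model sharpen the 4-month result?** With complete data and an unstructured covariance, the baseline-to-4-month contrast has the same estimate and standard error as the t-test. The gain is zero.

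**The case against.** The strongest reply has four parts.

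**The plan is not silent.** Section 9 does contain a trajectory model, and it plans descriptive analyses of all dependent variables; a table of means by visit would separate 6-4-5 from 6-6-5. The app also collects interference items and opioid use, and Section 7.3.2 foresees exploring longitudinal outcomes with it. This stands in part. A reader might infer that the 2-month survey is never used, or that early and late relief could never be told apart. The documents do not support either: the data are collected, carry-forward can bring them in, and a descriptive table could show them. But no such table is named, and app data come from an optional subset without FACT-G.

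**The endpoint time is already chosen.** Section 7.3 selects 4 months for the future trial and gives a reason. True, so the trends would inform that choice and no rule depends on them. The benchmarks concern consultation, procedure receipt and satisfaction.

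**A cohort contrast does not prove waning.** Visits run from enrolment, not from the procedure. The windows of 7-13 and 15-19 weeks put the two follow-ups 2 (15 - 13) to 12 (19 - 7) weeks apart. Consultation may take 4 weeks, and the benchmark asks for only half of evaluated patients to receive a procedure. This stands: the contrast describes the average course and cannot by itself show fading after a procedure.

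**A precision gain is tempting but not available here.** Averaging both follow-ups would multiply the standard error by √[((1 + rho)/2 + 1 - 2r) / (2(1 - r))], with r the baseline-to-follow-up correlation. For r = 0.4, rho = 0.7 this is √(1.05/1.20) = 0.935; for r = 0.5, rho = 0.5 it is √(0.75/1.00) = 0.866. That narrowing of about 6% to 13% belongs to a different estimand, which would also blur the shape of interest.

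**Conclusion.** The point holds as an analysis gap. The plan promises trends that its named survey analyses do not deliver: the only trajectory model covers app-reported pain, the post visit is undefined, and the 2-month BPI and FACT-G scores enter a named test only when carried forward. The reading by table and section needs no assumption; the size does. In the illustration, two opposite courses share a change of -1.0, and carry-forward of 10% to 40% of 4-month scores spreads the estimates to between -1.4 and -0.6.

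The opioid gap is of the same kind but has a different source: dose is a chart measure, so the unused information is the dated changes, not the 2-month survey. Self-reported opioid use at the surveys concerns adherence and breakthrough doses and does not by itself give MME.

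Importance is moderate. These outcomes are exploratory, the primary aims are unaffected, and no claim of better precision at 4 months should be made. The change is still worth making, because it lets the pilot answer a question it sets itself with data it already collects.

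**What to change.** In Section 9:

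1. Name 4 months as the post visit for the pre-post differences, in line with Section 7.3.
2. Add an exploratory repeated-measures mixed model for each of BPI severity, BPI interference and FACT-G, fitted to the observed scores without carry-forward, with visit (baseline, 2, 4 months) as a categorical factor and an unstructured covariance. Do not use a single linear slope.
3. Report the baseline-to-2, baseline-to-4 (headline) and 2-to-4-month mean changes with 95% confidence intervals and the number of surveys behind each. Describe them as whole-cohort changes timed from enrolment.
4. For opioid dose, use the dated medication changes in Section 7.3.1 to summarise MME by study month.

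Separately, reconcile the monthly surveys in Section 2.1 with the three-survey schedule in Sections 6.2, 7.1 and 7.3 and Table 3.

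The cost is a few sentences in Section 9, one correction in Section 2.1 and a few lines of code. The opioid summary also needs some derivation from the abstracted dates. No patients, visits or data items are added. The model relies on scores being missing at random given those observed, which should be stated.

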## 2.2 Background and Significance

**Pain is a common, distressing, and costly complication of cancer.** Pain affects approximately half of all patients receiving cancer treatment, a third of survivors, and up to 90% of those in the terminal phase of illness. Poorly controlled pain has devastating consequences to cancer patients' quality of life, mood, relationships, and functional wellbeing. Pain is also among the most frequent reasons cancer patients receive emergency department and hospital-based care, making better pain management a priority for healthcare systems, in addition to patients and their families.

**For patients living with advanced incurable cancers, the burden of pain is particularly great.** Cancer is the second leading cause of mortality in the US, with 606,880 expected to die from it in 2019. According to a 2016 meta-analysis, the prevalence of pain among patients with advanced stage cancers is 66.7%, with rates exceeding 90% for several common cancer types (e.g. pancreatic) and near end-of-life. Advanced cancer pain can be notoriously severe as tumors invade nearby nerves, bones, and other tissues. Moreover, poorly controlled pain poses a significant burden to patients' emotional wellbeing, and their ability to function physically and to fulfill important life roles. Due to recent therapeutic advances (e.g. immunotherapy, targeted therapies), patients are living much longer with their disease, and can consequently live for years with chronic cancer pain. It is therefore essential that pain be managed in a way that enables patients to remain engaged in life.

**Systemic opioids are considered the cornerstone of treatment for advanced cancer pain; however, medical management alone is often inadequate.** Up to 60% of advanced cancer patients experience inadequate pain relief despite access to opioids. Moreover, several cancer pain syndromes (e.g. visceral, neuropathic) are characteristically opioid-resistant – leaving some patients on extremely

high doses with only marginal benefit. Side effects including constipation, fatigue, sedation, and mood changes are extremely common, and can prevent patients from engaging in meaningful aspects of their lives. Patients are often given multiple pain medications, at variable doses, making self-management confusing and difficult. Moreover, there is a literature to suggest that opioids may promote tumor progression and shorten patients' survival. In light of growing safety concerns about opioids, many have called for further research into non-pharmacologic strategies to manage advanced cancer pain.

Recognizing the limitations of pharmacologic management for advanced cancer pain, **expert organizations including the National Comprehensive Cancer Network (NCCN) recommend consideration of interventional pain management strategies** such as regional neurolysis procedures, intrathecal targeted drug delivery (TDD), vertebroplasty, or percutaneous tumor ablations. Randomized trials suggest that many of these approaches are effective for cancer pain. For example, celiac neurolysis has been found to improve pain, and potentially reduce opioid consumption among patients with pain from advanced pancreatic tumors. TDD has been shown in a randomized study to improve pain and reduce opioid consumption and toxicity and possibly extend survival, with a recent retrospective database analysis suggesting cost savings. Unfortunately, patients are usually referred for interventional pain management strategies very late in the disease course, often near the end-of-life, or during a hospitalization for refractory pain. By this time, many patients have been suffering from poorly managed pain for many months, and their pain syndromes may be relatively unresponsive to any treatment because of prolonged exposure to high-dose opioids.

**Health systems factors likely play a significant role in limiting advanced cancer patients' access to interventional pain management.** First, there are no standardly agreed upon triggers for intervention pain management referral, leading to very late referrals when patients may not even be eligible for certain procedures such as TDD. Second, most interventional pain management specialists operate outside of cancer clinics, making oncologists largely unfamiliar with their capabilities and scope of practice. Third, many pain management specialists lack specific experience with advanced cancer patients, or guidelines needed to integrate interventional techniques into these patients' care. These barriers call for healthcare delivery research to evaluate specific referral processes and treatment algorithms to integrate interventional strategies into the care of advanced cancer patients.

PROTOCOL TITLE: Randomized Clinical Trial of Early Intervention Pain Management for Patients with Advanced Cancers  
Version 4.0, [October 27, 2023]

Our overarching hypothesis is that early referral to pain management specialists and systematic consideration of interventional pain management strategies, will improve pain severity, physical functioning, and quality of life among patients with pain from advanced solid malignancies. We also hypothesize that early referral will minimize patients' reliance on systemic opioids, reduce opioid toxicity, unplanned emergency department and hospital-based care for pain, and potentially prolong survival.

This will be a single arm pilot study in which we will identify patients with advanced malignancies who have cancer-related pain, who are not yet on high-dose opioids, and we will arrange for early referral to an interventional pain management specialist at a large center with expertise in cancer pain management. We will evaluate metrics of study feasibility/acceptability needed to plan for a future randomized trial. We will also assess key proximal and distal outcomes needed for a future randomized trial, such as time to completion of the pain management referral, the numbers and types of interventional pain strategies recommended (e.g. nerve blocks, ITT), the proportion of patients accepting those therapies, trajectories of pain severity/interference, opioid doses, and pain-related ED visits and hospitalizations.

